9.4.4 Supportive analyses

Not applicable.

9.5 Analysis of secondary variables

9.5.1 Efficacy variables

- Mean change in CRT (μm) by Optical coherence tomography at 12th month from baseline
- Mean no. of injections over a 12-month treatment period
- Mean no. of visits over a 12-month treatment period
- Proportion of patients who gained ≥ 0 , ≥ 5 , ≥ 10 and ≥ 15 letters in BCVA at 12th month
- Incidence of adverse events (AEs) and serious AEs (SAEs), by ophthalmic examinations and IOP measurements, and by changes in vital signs and laboratory parameters over the 12-month assessment period.
- Mean change in VFQ25 scores at 12th month from baseline

9.5.2 Safety variables

All safety evaluations will be summarized and submitted for each visit per treatment arm.

All adverse events will be summarized per treatment arm, as patient numbers and per cents for any adverse event experience and adverse events for each system organ class will be summarized. All information collected (i.e.: severity or grade or causality assessment) will be summarized. Deaths and SAEs requiring early discontinuation will be summarized separately.

Laboratory details will be submitted as the descriptive statistics of the core data and for changes in the baseline data for each treatment arm (mean, median, standard deviation, interval) will be analyzed by highlighting the clinically notable changes.

Vital signs will be summarized and descriptive statistics will be given for heart rate and pulse in a sitting posture including the baseline changes.

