B=Baseline; EoT=End of the Trial; BCVA= Best Corrected Visual Acuity; VFQ-25=Visual Function Questionnaire

- a) Blood pressure and pulse will be measured after the injection of the study medication (if applicable)
- b) Urine pregnancy test will only be performed to WOCBP. Additional tests may be performed as a decision of the investigator.
- c) Site staff will contact with the patient via phone 1-3 days after the study medication injection to inquire if there is any loss of vision, eye ache, unnormal redness or occurrence of any new ocular symptom. Patients will visit the site for an unscheduled visit if needed.
- d) If the lesion is active, according to the Royal College of Ophthalmology
- e) Ophthalmologic examination: slit lamp and fundus examination will be performed before injection (if applicable)
- f) IOP measurement with tonometry will be performed before injection and after 60 minutes of injection.
- g) FFA is mandatory at month 0 and 12 and will be performed according to the investigators's desicion at the other visits.
- h) Rescue laser treatment will be performed after the first three injection and according to the criteria described in the protocol.
- i) VFQ-25 will be questioned in either of the first two screening visits.

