6.1 Information to be collected on screening failures

All patients who have signed informed consent but not entered into the next epoch will have the study completion page for the screening epoch, demographics, inclusion/exclusion, and SAE data collected. Adverse events that are not SAEs will be followed by the investigator and collected only in the source data.

For all patients who have signed informed consent and are entered into the next epoch of the study will have all adverse events **occurring after informed consent is signed** recorded on the Adverse Event CRF. Adverse events will be tracked in the baseline visit (visit 2) at day 0.

Investigators will have the discretion to record abnormal test findings on the medical history CRF whenever in their judgment, the test abnormality occurred prior to the informed consent signature.

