7.1 Adverse events

An adverse event (AE) is any untoward medical occurrence (i.e., any unfavorable and unintended sign [including abnormal laboratory findings], symptom or disease) in a subject or clinical investigation subject *after providing written informed consent* for participation in the study. Therefore, an AE may or may not be temporally or causally associated with the use of a medicinal (investigational) product.

The occurrence of adverse events should be sought by non-directive questioning of the patient at each visit during the study. Adverse events also may be detected when they are volunteered by the patient during or between visits or through physical examination, laboratory test, or other assessments.

Abnormal laboratory values or test results constitute adverse events only if they fulfill at least one of the following criteria:

- they induce clinical signs or symptoms,
- they are considered clinically significant,
- they require therapy.

Clinically significant abnormal laboratory values or test results should be identified through a review of values outside of normal ranges/clinically notable ranges, significant changes from baseline or the previous visit, or values which are considered to be non-typical in patient with underlying disease. Investigators have the responsibility for managing the safety of individual patient and identifying adverse events. Alert ranges for labs and other test abnormalities are included in Appendix 1.

Adverse events should be recorded in the Adverse Events CRF under the signs, symptoms or diagnosis associated with them accompanied by the following information.

- the CTCAE grade

If CTCAE grading does not exist for an adverse event, use 1=mild, 2=moderate, 3=severe, and 4=life-threatening. CTCAE Grade 5 (death) is not used, but is collected in other CRFs (Study Completion, Death/Survival).

- its relationship to the study treatment (no/yes)
- its duration (start and end dates) or if the event is ongoing an outcome of not recovered/not resolved should be reported.
- whether it constitutes a serious adverse event (SAE)
- action taken regarding study treatment
- whether other medication or therapies have been taken (concomitant medication/non-drug therapy)
- its outcome (not recovered/not resolved; recovered/resolved; recovering/resolving, recovered/resolved with sequelae; fatal; or unknown)

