9.1 Analysis sets

The Safety population will consist of all patients who received at least one intravitreal injection of ranibizumab.

All analyses will be performed using the Safety population

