6.15 SAFETY ASSESSMENT

6.15.1 Adverse / Serious Adverse Events

The list of the Adverse / Serious Adverse Events (SAE) reported in each visit will be provided. All adverse events will be examined regarding the visits they occurred, severity (mild, moderate, severe), relationship with the drug (suspected, not suspected), outcome (continuing, resolved), actions taken (no action taken, dose adjusted/dosing interrupted, additional treatment given, non-pharmacological treatment given, hospitalized), additional treatments if applicable, time between hospitalization and discharge dates, and length of hospital stay.

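### The by-arm adverse event tables have no onset limit, so they count events from informed consent onwards, including events before randomisation and first injection; the effect is probably small and the remedy is nearly free.

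*Protocol*

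**What the plan says.** **When an event counts.** Protocol 7.1 defines an adverse event as an untoward occurrence "after providing written informed consent". Protocol 6.1 has the AE CRF hold, for patients who go beyond screening, all events "occurring after informed consent is signed", and adds: "Adverse events will be tracked in the baseline visit (visit 2) at day 0". Protocol 7.2 likewise starts SAE reporting at consent.

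**When treatment starts.** The design figure (Protocol 3.1) and the schedule (Protocol 6) put Visit 1 on Day -7 to -1. Randomisation and the first injection are at Visit 2. Protocol 6.4 places an angiogram at Screening/Visit 1, and footnote g to the schedule confirms: "FFA is mandatory at month 0 and 12".

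**Who is analysed.** Protocol 9.1: "The Safety population will consist of all patients who received at least one intravitreal injection of ranibizumab".

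**What is tabulated.** Protocol 9.5.2: "All adverse events will be summarized per treatment arm, as patient numbers and per cents for any adverse event experience". It also promises summaries of severity and causality, and safety summaries by visit. SAP 6.15.1: "All adverse events will be examined regarding the visits they occurred", with severity, relationship to drug, outcome and action taken. Neither document defines a treatment-emergent event or gives an onset date from which the by-arm counts begin.

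**The concern.** Read as written, an event that begins after consent but before the patient has an arm, and before any study injection, is counted in the incidence of the arm later assigned. Neither regimen could have caused it. Such events are possible in this trial: a mandatory angiogram is done in that gap, and Protocol 5.5.8 permits treatment to prevent nausea from the fluorescein.

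What is at stake is the descriptive safety comparison. The study title names safety alongside efficacy, and safety is a secondary objective. Background events common to both arms raise both percentages and make the regimens look more alike than they are on treatment. The primary endpoint is not touched.

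**Working it through.** **Step 1: is there any onset limit?** Four places might supply one.

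- *Safety population (Protocol 9.1).* It selects patients by whether they were injected. It does not select events by date.
- *Schedule of assessments (Protocol 6).* The AE row begins at Visit 2. Section 6.1 still records events from consent and has them tracked at that visit, so the row shows where they are picked up, not where counting starts.
- *The 12-month assessment period (synopsis and Protocol 9.5.1).* Its start is not defined, and 9.5.2 does not repeat it.
- *Presentation by visit (Protocol 9.5.2, SAP 6.15.1).* The any-event count per arm in 9.5.2 carries no visit restriction.

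None of them removes pre-injection events from the by-arm incidence.

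**Step 2: can the events be separated with the data collected?** Protocol 7.1 requires start and end dates. Visit 1 is at least one day before baseline, and the schedule shows no angiogram at Visit 2. A reaction on the day of the screening angiogram therefore has a start date before Day 0. Only events that begin on Day 0 itself are ambiguous, because dates without times cannot place them before or after the injection.

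**Step 3: size.** The documents give no adverse event rates, so every rate below is an assumption. Let p be the on-treatment incidence and q the share of patients with an event between consent and first injection. If the two are independent:

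- tabulated incidence = 1 - (1-p)(1-q)
- tabulated difference = (1-q) × (true difference)

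To set q, assume a constant event rate, with 7 days of screening (the longest scheduled window) against 360 days of treatment: q = 1 - (1-p)^(7/360).

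- p = 20%: q = 1 - 0.80^0.01944 = 0.43%
- p = 40%: q = 1 - 0.60^0.01944 = 0.99%

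Applied to an assumed true 20% v 10% (difference 10 points, ratio 0.50), with 43 patients per arm from the sample size section. The last three rows are larger values of q, for sensitivity only:

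| q | Tabulated incidence | Difference (points) | Ratio | Patients per arm with a pre-injection event (43 × q) |
|---|---|---|---|---|
| 0.43% | 20.3% v 10.4% | 9.96 | 0.51 | 0.2 |
| 0.99% | 20.8% v 10.9% | 9.90 | 0.52 | 0.4 |
| 2% | 21.6% v 11.8% | 9.8 | 0.55 | 0.9 |
| 5% | 24.0% v 14.5% | 9.5 | 0.60 | 2.2 |
| 10% | 28.0% v 19.0% | 9.0 | 0.68 | 4.3 |

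The net addition to each arm's count is below the last column, because some of these patients also have a later event; the tabulated percentages already allow for that.

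Protocol 4.1 lets the eligibility imaging fall up to 28 days before baseline treatment. If consent were that early, the same formula with 28/360 gives q of 1.7% (p = 20%) to 3.9% (p = 40%), which lies inside the table.

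**Step 4: against sampling error.** With 43 per arm and 20% v 10%, the standard error of the difference is √[(0.20×0.80 + 0.10×0.90)/43] = √(0.25/43) = 7.6 points, so a 95% interval is about ±15 points. A shift of 0.04 to 0.1 point (q of 0.4% to 1%), or even 1 point (q of 10%), is small beside that.

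**The case against.** The case that this matters little is strong, and most of it stands.

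- *Balance.* The events precede randomisation, so they are balanced between arms in expectation. A reader might infer that one regimen is unfairly charged; the documents do not support that. What remains is slight inflation in both arms, dilution of the contrast and some chance noise.
- *Separability.* A reader might infer that reactions to the screening angiogram cannot be told apart from first-injection reactions because both are picked up at Visit 2. The start dates required by Protocol 7.1 separate them.
- *Rate.* A reader might assume that 2% to 10% of patients have a pre-injection event. Nothing in the documents supports this for a window of 1 to 7 days. Permission to prevent fluorescein nausea is not a reaction rate. Positive correlation between screening and on-treatment events would reduce the inflation further.
- *Scale.* The ratio moves most, but the plan specifies no between-arm ratio, test or interval for adverse events; its tables are descriptive.
- *Causality.* Relationship to treatment is also summarised, and an event before any drug should be classed as unrelated there.
- *Reach of the remedy.* Angiography is also mandatory at month 12 and discretionary at other visits. Reactions to those would still be counted after the change.

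What does not fall is the counting rule. Both documents take all adverse events, the definition starts at consent, and no text sets an onset limit. The causality summary is additional and rests on investigator judgement in an open-label study; it does not change the any-event count.

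**Conclusion.** The point holds as a minor one. Followed literally, the plan puts events from before randomisation and before the first injection into the by-arm AE and SAE incidence. No regimen is favoured. Absolute incidence is slightly inflated in both arms, and the risk difference shrinks by the factor (1-q).

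On the assumptions of a constant rate, a 7-day window, 20% to 40% on-treatment incidence and independence, q is about 0.4% to 1%, and an assumed ratio of 0.50 becomes about 0.51-0.52. The shift would be larger only if reactions to the screening angiogram were common, on which the documents are silent. The documents do not support a conclusion that a real safety difference between the regimens would be materially hidden. The reason to act is that the stated rule is easily replaced by a better one.

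**What to change.** In Protocol 9.5.2 and SAP 6.15.1, state that the by-arm AE and SAE tables include only events that start or worsen on or after the first study injection, identified from the start dates already collected. List events between consent and first injection separately, without attribution to an arm.

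A before/after-injection tick on the AE CRF for events starting on Day 0 is optional, since only those are ambiguous. Without it, state that Day 0 events are counted as on or after the injection.

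Cost: one or two sentences in each document and one extra listing, plus a CRF box if the option is taken. No visits, patients or assessments are added, and no safety data are lost.

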9.5.3 Resource utilization

Not Applicable

9.5.4 Health-related Quality of Life

Quality of Life variables will include the total score and sub-scores of the Visual Function Questionnaire – 25 (VFQ – 25) Descriptive statistics will be given including the changes according to the baseline.

9.5.5 Pharmacokinetics

Not Applicable

9.5.6 Pharmacogenetics/pharmacogenomics

Not Applicable

9.5.7 Biomarkers

Not Applicable

9.5.8 PK/PD

Not Applicable

9.6 Interim analyses

NA

9.7 Sample size calculation

A sample size of 86 (43 for each treatment arm) can achieve 90% power to detect non-inferiority limit of 5 letter between treatment arm when significance level of the test is 0.025 and the mean (standard deviation) letter change of labeled regime arm will be around 7 (7). To eliminate the effects of incomplete data which are expected in 1 year follow-up period, a priori 20% of drop-out rate is accepted; therefore at least 104 patients (52 for each treatment arm) will be included to the study.

10 Ethical considerations**10.1 Regulatory and ethical compliance**

This clinical study was designed and shall be implemented and reported in accordance with the ICH Harmonized Tripartite Guidelines for Good Clinical Practice, with applicable local regulations (including European Directive 2001/20/EC, US Code of Federal Regulations Title 21, and Japanese Ministry of Health, Labor, and Welfare), and with the ethical principles laid down in the Declaration of Helsinki.

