Population	The study population will consist of male and female patients (over 18 years old) admitted to hospital with Type 1 or Type 2 diabetes mellitus (according to ADA or WHO guidelines) with HbA1c not more than 12.0% at screening (Visit 1). Patients should be on diet, exercise, and/or pharmacological treatment for diabetes and should have a visual impairment due to focal or diffuse macular edema with center involvement in at least one eye, as demonstrated with color fundus photography, fluorescein angiography and OCT within 28 days of the baseline treatment. It is aimed to randomize a total of 86 patients in approximately 12 centers in Turkey. Since a 20% screening failure rate is expected, 104

	patients have to be screened.
Inclusion criteria	
 1. Written informed consent must be obtained before any assessment is performed. 2. Male or female patients >18 years of age who have signed an informed consent 3. Patients with Type 1 or Type 2 diabetes mellitus (according to ADA or WHO guidelines) with HbA1c not more than 12.0% at screening (Visit 1). Patients should be on diet, exercise, and/or pharmacological treatment for diabetes. 4. Patients with visual impairment due to focal or diffuse macular edema with center involvement in at least one eye, as demonstrated with color fundus photography, fluorescein angiography and OCT within 28 days of the baseline treatment. If both eyes are eligible, the one with the worse visual acuity, as assessed at Visit 1, will be selected for study treatment unless, based on medical reasons, the investigator deems the other eye the more appropriate candidate for study treatment. The study eye must fulfill the following criteria at Visit 1: 
 • BCVA score between 78 and 39 letters, inclusively, using ETDRS-like visual acuity testing charts at a testing distance of 4 meters (approximate Snellen equivalent of 20/32 to 20/160) • Decrease in vision is due to DME and not due to other causes, in the opinion of the investigator

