Efficacy assessments	
Mean change in Best-corrected visual acuity (BCVA) with ETDRS-like chart at a starting distance of 4 meters, at 12th month from baselineMean change in CRT (μm) by Optical coherence tomography at 12th month from baselineMean no. of injections over a 12-month treatment periodMean no. of visits over a 12-month treatment periodProportion of patients who gained ≥0, ≥5, ≥10 and ≥15 letters in BCVA at 12th monthMean change in VFQ25 scores at 12th month from baseline
Safety assessments	
Incidence of adverse events (AEs) and serious AEs (SAEs), by ophthalmic examinations and IOP measurements, and by changes in vital signs and laboratory parameters over the 12-month assessment period.
Other assessments	There is no other planned analysis to be performed for this study.
Data analysis	A sample size of 86 (43 for each treatment arm) can achieve 90% power to detect non-inferiority limit of 5 letter between treatment arm when significance level of the test is 0.025 and the mean (standard deviation) letter change of labeled regime arm will be around 7 (7). To eliminate the effects of incomplete data which are expected in 1 year follow-up period, a priori 20% of drop-out rate is accepted; therefore at least 104 patients (52 for each treatment arm) will be included to the study.
Key words	Optic Coherence Tomography, Diabetic Macular Edema, Ranibizumab, Tolerability, Safety, Wait and Extend

1 Introduction

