3.5 Risks and benefits

The risk to subjects in this trial will be minimized by compliance with the inclusion/exclusion criteria, close clinical monitoring, since the study has been designed in a similar approach to a newly completed study which was completed with no major safety and tolerability concerns there are no unknown risks to *Ranibizumab* which may be serious and unforeseen.

4 Population

The study population will consist of male and female patients (over 18 years old) admitted to hospital with Type 1 or Type 2 diabetes mellitus (according to ADA or WHO guidelines) with HbA1c not more than 12.0% at screening (Visit 1). Patients should be on diet, exercise, and/or pharmacological treatment for diabetes and should have a visual impairment due to focal or diffuse macular edema with center involvement in at least one eye, as demonstrated with color fundus photography, fluorescein angiography and OCT within 28 days of the baseline treatment. It is aimed to randomize a total of 86 patients in approximately 12 centers in Turkey. Since a 20% screening failure rate is expected, 104 patients have to be screened.

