5 ANALYZED POPULATIONS

The study population will include male and female patients (above 18 years of age) who were admitted with Type 1 or Type 2 diabetes mellitus (according to ADA or WHO guidelines) with HbA1c values not exceeding 12.0% at screening (Visit 1). Patients should be following a diet, exercise and/or pharmacologic therapy for diabetes mellitus and should have vision loss for focal or diffuse macular edema with central involvement in at least one eye as demonstrated by color fundus photography, fluorescein angiography and OCT over a period of 28 days prior to initial treatment. A total of 86 patients from 12 centers in Turkey are expected to be randomized. Because a screening failure rate of 20% is anticipated, 104 patients will be needed to be screened.

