5.1. SAMPLE SIZE CALCULATION

A sample size of 86 patients (43 patients in each treatment arm) will provide 90% power to determine a non-inferiority margin of 5 letters between the treatment arms with a significance level of 0.025 for the test, and the mean (standard deviation) letter change of the prescribing information regimen arm will be approximately 7 (7). A 20% discontinuation rate is initially assumed in order to account for the missing data expected for a follow-up period of 1 year; thus, at least 104 patients (52 patients in each treatment arm) will be included in the study.

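### The number to randomise is 86 in some sections and 104 in others, because 104 serves both as the number screened and as the number included

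*Protocol*

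**What the plan says.** Two sets of sections give two accounts of the same numbers.

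**Sample-size sections** (Protocol 9.7, the Data analysis row of the synopsis, SAP 5.1). The power statement is tied to 86: "A sample size of 86 (43 for each treatment arm) can achieve 90% power to detect non-inferiority limit of 5 letter between treatment arm". An allowance for incomplete data over one year of follow-up is then added: "a priori 20% of drop-out rate is accepted; therefore at least 104 patients (52 for each treatment arm) will be included to the study". SAP 5.1 repeats it: "thus, at least 104 patients (52 patients in each treatment arm) will be included in the study".

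**Population sections** (Protocol section 4, the Population row of the synopsis, SAP section 5). Here 86 is the randomisation target: "It is aimed to randomize a total of 86 patients in approximately 12 centers in Turkey". The same 104 appears for a different reason: "Since a 20% screening failure rate is expected, 104 patients have to be screened". SAP section 5 agrees: "A total of 86 patients from 12 centers in Turkey are expected to be randomized", again with 104 to be screened.

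The conflict therefore occurs inside the synopsis, inside the protocol body and inside the SAP.

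**The concern.** Screening failure happens before randomisation and drop-out happens after it. A trial that expects 20% of each needs two successive allowances. This plan makes one, from 86 to 104, and counts it against whichever loss the section is discussing.

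The randomisation target decides when recruitment stops, and the two accounts differ by 18 patients. A team working from Protocol section 4 or SAP section 5 stops at 86 and has no cover for the drop-out that Protocol 9.7 and SAP 5.1 expect. A team working from the sample-size sections continues to 104. No interim analysis or sample-size review is planned that would catch a shortfall, and Protocol 9.4.3 gives no imputation rule, only close monitoring of sites. Patients without month-12 BCVA may therefore simply be missing from the primary comparison.

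**Working it through.** **Inputs from the documents.** Margin 5 letters, SD 7, significance level 0.025, power 90%, 86 patients (43 per arm), 20% drop-out (Protocol 9.7, SAP 5.1); 20% screening failure (Protocol section 4, SAP section 5); 1:1 allocation (Protocol 5.3).

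**Assumptions the documents do not state.** SD 7 in both arms, true difference 0, 0.025 read as one-sided, and analysis only of patients with month-12 data.

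**Step 1: reproduce the plan's 86.** The normal approximation is n per arm = 2(z₀.₉₇₅ + z₀.₉₀)² × SD² / margin² = 2 × (1.960 + 1.2816)² × 49/25 = 41.2, so 42. With the noncentral t distribution, 42 per arm gives 89.9% and 43 gives 90.6%, so 43 is the smallest number that reaches 90%. The plan's 86 reproduces. Reading 0.025 as two-sided would need 49 (normal) or 50 (t) per arm, which does not match. The stated 90% therefore belongs to 86 *evaluable* patients.

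**Step 2: reproduce the plan's 104.** 86 × 1.2 = 103.2, rounded up to 104 as two arms of 52. Allowing for a 20% loss requires division: 86/0.8 = 107.5, so 108. As written, 104 leaves 86 only if loss is at most 1 − 86/104 = 17.3%.

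**Step 3: test whether both uses of 104 can hold.** 104 screened with 20% failure gives 104 × 0.8 = 83.2 randomised, below both 86 and 104. A further 20% drop-out leaves 83.2 × 0.8 = 66.6, about 33 per arm, with power 81.5% (t) or 82.7% (normal). The two uses cannot both hold.

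**Step 4: power under each target.** The noncentrality is 5 / (7 × √(2/n)), with n evaluable per arm.

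| Randomised | Loss | Evaluable per arm | Power (t) | Power (normal) |
|---|---|---|---|---|
| 86 | 0% | 43 | 90.6% | 91.2% |
| 86 | 5% | 40.85 | 89.0% | 89.8% |
| 86 | 10% | 38.7 | 87.3% | 88.1% |
| 86 | 15% | 36.55 | 85.4% | 86.3% |
| 86 | 20% | 34.4 | 83.1% | 84.2% |
| 104 | 20% | 41.6 | 89.6% | 90.3% |

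**Step 5: screening numbers with 20% failure.** For 104 randomised, 104/0.8 = 130. For 86 randomised, 86/0.8 = 107.5, so 108.

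**The case against.** The best defence is that the sections differ in force. Protocol 9.7 and SAP 5.1 set a minimum and give a power rationale, whereas the population sections state an aim or an expectation. A reader could let the sample-size section govern. That is a sensible guess, but neither document says so, and Protocol section 4 is where a recruiting team would look.

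A second defence reads *included* as consented. The glossary places enrolment at consent, and Protocol 10.2 links inclusion to consent. This does not survive the text. The 104 is split as 52 per arm, and under Protocol 5.3 a patient has an arm only after randomisation at Visit 2. The stated reason is also incomplete follow-up, which comes later still.

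Third, the fall to about 83% needs several things together: recruitment stops at 86, the full 20% is lost, and those patients are not analysed. Protocol 5.5.9 says patients who stop the drug are not to be counted as withdrawn and encourages them to attend the final-visit assessments. Loss of 5% to 10% would cost only about 2 to 3 points. This stands as a limit on the size of the effect, although 20% is the plan's own figure.

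Fourth, the power figures are for a comparison of means against 5 letters, whereas SAP 6.14.1 names a Mann-Whitney U test and states no margin there. That is fair. The figures apply to the basis that reproduces the plan's own 90%, not to the test as the SAP describes it.

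Finally, multiplying by 1.2 instead of dividing by 0.8 costs about 1 point of power and adds nothing to the seriousness.

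**Conclusion.** The concern holds. The randomisation target is contradictory in both documents, and the same 104 is assigned to two different losses. If 86 are randomised and the planned 20% are lost and not analysed, about 69 remain (86 × 0.8 = 68.8). The risk of missing non-inferiority against the 5-letter margin then rises from about 10% to about 17%. At 5% to 15% loss that risk is about 11% to 15%. If 104 are randomised, about 83 remain (104 × 0.8 = 83.2) and power is about 90%. The power figures rest on the assumptions listed in the working; the contradiction itself rests on none of them. It should be fixed, but it does not undermine the design, because one of the two stated targets is adequate.

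**What to change.** State one number each for screened, randomised and evaluable patients. Use the same three in both synopsis rows, Protocol section 4, Protocol 9.7, SAP section 5 and SAP 5.1. Apply screening failure and drop-out as separate steps, and state the assumptions behind the power figure: SD in each arm, true difference, sidedness and who is analysed. The sponsor has two main choices.

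- **Keep the sample-size sections:** 104 randomised (52 per arm), about 83 evaluable, power about 90%, about 130 screened. Change the text that randomises 86 in the synopsis, Protocol section 4 and SAP section 5.
- **Keep the population sections:** 86 randomised, about 69 evaluable, power about 83%, about 108 screened. Remove the text that includes 104 from the synopsis, Protocol 9.7 and SAP 5.1.

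If the sponsor wants 86 evaluable after a full 20% loss, division at both steps gives 108 randomised and 108/0.8 = 135 screened.

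The document cost is wording only. The practical cost is either a rise in expected screening from 104 to about 130 (135 for the last option), or an acknowledged power of about 83% with about 108 screened.
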